This technological revolution has progressively affected the health world. An increasing number of medical APP have been designed in the last years, few directly managed from health care providers from public or private centers. ThemHealth (Mobile Health) APP could led to a simpler, real-time connection between patients and health care professionals alongside with a bidirectional data flow and a steadily monitorization of patients' evolution that could obtain a better preoperative follow-up without increasing the costs [24-26].

The present randomized clinical trial aims to prove the safety and efficacy of an interactive mobile application (Care4Today®) to obtain sufficient weight loss and empower patients with morbid obesity before being submitted to a gastric by-pass.

HYPOTHESIS:

Main hypothesis: The preoperative use of the Care4Today (C4T) application in addition to standard protocol, in patients with a grade II-III obesity (BMI between 35 and 50 Kg/m²) achieves greater preoperative weight loss than standard protocols.

Secondary Hypothesis: Use of the Care4Today (C4T) application in the preoperative setting achieves:

- less intra- and post-operative complications at 30 and 90 days;
- less technical complexity and duration of surgery;
- better patients' information and satisfaction;
- better medical team coordination and satisfaction;
- better weight loss outcomes at mid-term (1, 3 and 5 years).

AIMS:

Main goal: To compare patients' preoperative weight loss after using the C4T APP in addition to standard protocol versus the standard preoperative protocol.

Secondary goals:

1. Compare patients' information / satisfaction using the APP vs. standard protocol.
2. Compare complications in the immediate postoperative period (30- and 90-days post-intervention) after the preoperative use of APP vs. standard protocol.
3. Compare medical team coordination / satisfaction using the APP vs. standard protocol.
4. Compare patients' weight loss 3 months after surgery using the APP vs. standard protocol.

STUDY DESIGN: Randomized Clinical Trial to assess the safety and efficacy of a mobile application to monitor patients undergoing bariatric surgery.

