S. All the contents in the APP have been properly selected and modified by the multidisciplinary team. The day of surgery all the data about weight loss, patient and medical team satisfaction will be collected. Then, patients will be followed in observation of our standard postoperative protocol to assess the 30th and 90th postoperative morbidity and mortality alongside with weight loss evolution. The PhD student has been directly involved in the APP design and contents creation. He will perform the preoperative presential meeting to provide and explain the APP functioning to the patients in the APP group. Furthermore, he will collect the data on the day of surgery, during surgery and will be directly involved in postoperative follow-up of all patients.

STUDY POPULATION:

Inclusion criteria:

- Patients older than 18 and younger than 65 years who meet criteria to undergo bariatric surgery
- BMI between 35 and 50 kg/m² and indication of one-time surgery
- Signing the informed consent of the study
- Patient suitable for laparoscopic surgery
- Patient who demonstrates accessibility to a smartphone and basic digital competence (Appendix 1).

Exclusion criteria:

- Previous bariatric surgery
- Two-step surgery
- Patient without resources to access the use of a Smartphone or without basic digital competence
- Contraindication for surgery
- Other surgical procedures associated with the same intervention

Retirement criteria:

- None

EXPERIMENTAL TREATMENT: Use of a mobile application to accompany and empower patients in the preoperative period.

EVALUATION CRITERIA:

Main criteria (for the main goal): Preoperative percentage of excess weight lost (%EWL), considering ideal BMI = 25, will be recorded.

Following the follow-up protocol in General Surgery Outpatient Consultations, patients' weight will be measured 4 months before surgery and on the same day of surgery; then at 3, 6 and 12 months, and then every year up to 5 years of follow-up to calculate BMI and percentage of overweight lost, percentage of BMI lost, total weight and BMI lost.

Secondary criteria (for secondary goals):

1. Patients' information and satisfaction using the APP vs. standard protocol will be evaluated using approved questionnaire (appendix 2, appendix 3);

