2. Morbidity and mortality: morbidity and mortality will be evaluated using the prospective database of the Bariatric Surgery Unit and the electronic medical record of each patient. All perioperative aspects related to the surgery will be reviewed. Complications will be recorded according to the Clavien-Dindo classification.
3. Metabolic comorbidities: Comorbidities related to metabolic syndrome and morbid obesity will be recorded to study their evolution up to 5 years after the intervention: DM2, hypertension, DL and OSAS.
4. Medical team coordination and satisfaction using the APP vs. standard protocol will be evaluated during multidisciplinary committee.
5. Patients weight loss 3 months after surgery will be evaluated using the prospective database of the Bariatric Surgery Unit and the electronic medical record of each patient.
6. Nutritional and metabolic deficiencies: The analytical studies performed each year on these patients will be evaluated to detect possible deficiencies: protein, iron, phosphocalcic, fat-soluble vitamins and trace elements.

STUDY DURATION:

The study is expected to begin in October 2022

Patient recruitment period is expected from October 2022 to March 2024.

Preoperative follow-up will be completed the day of surgery.

Mid-term follow-up (2 years) will be completed in March 2026.

Long-term follow-up (5 years) will be completed in March 2029.

SAMPLE SIZE:

The sample size was calculated in 142 patients divided into two groups of 71 patients each. It was calculated by comparing a hypothetical reduction of ≥ 5 kg in 55% of patients in the C4T group vs in 39% of patients in the control group [27] with a possible loss of 16% of patients, a confidence level of 95%, and statistical power of 80%.

STATISTICAL ANALYSIS:

Continuous variables will be expressed as mean \pm standard deviation or median (interquartile range) as appropriate. Differences between both techniques will be evaluated using a parametric test (χ^2 for categoric variables and t test for continuous variables). We'll use the IBM-SPSS Statistics Version 20 computer software to analyse all the statistics. A p value < 0.05 will be considered statistically significant.

PERSONAL DATA PROTECTION / CONFIDENTIALITY / ETHICAL ASPECTS:

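### The 3-month and 1-, 3- and 5-year weight comparisons have only a t test and no missing-data method; a repeated-measures model would recover some precision and limit drop-out bias

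*Combined protocol and SAP*

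**What the plan says.** All references are to the combined protocol and SAP.

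- **Schedule (Evaluation Criteria, main criteria).** Before the operation, "weight will be measured 4 months before surgery and on the same day of surgery"; afterwards, "then at 3, 6 and 12 months, and then every year up to 5 years of follow-up". The postoperative visits are therefore 3, 6 and 12 months and 2, 3, 4 and 5 years. Several weight and BMI measures are derived from them.
- **Comparisons intended.** The secondary hypothesis expects "better weight loss outcomes at mid-term (1, 3 and 5 years". The secondary goals under Aims list one postoperative weight comparison: "weight loss 3 months after surgery using the APP vs. standard protocol". Four postoperative time points are thus named for comparison: 3 months and 1, 3 and 5 years.
- **Method (Statistical Analysis).** The tests are χ² "for categoric variables and t test for continuous variables", and "A p value < 0.05 will be considered statistically significant". The section names no repeated-measures model, analysis population or missing-data rule.
- **Attrition (Sample Size).** The calculation allows "with a possible loss of 16% of patients, a confidence level of 95%, and statistical power of 80" per cent. That loss figure serves the preoperative calculation. The plan makes no projection of attrition to 5 years.

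**The concern.** A two-sample t test at a given visit can use only the patients who have a weight at that visit. Someone seen up to year 3 and then lost adds nothing to the year-5 comparison, although the earlier weights say a good deal about the missing one. Two things are at stake.

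1. **Precision.** Information already collected is not used.
2. **Bias.** If patients who lose little weight tend to stop attending, the remaining sample looks better than the randomised one. If this happens more in one arm, the arm difference is distorted. Selective loss of poor responders from the control arm would hide a benefit of the app; the same loss from the app arm would push the estimate the other way.

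These are the data on which the 1-, 3- and 5-year hypotheses will be judged.

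**Working it through.** The plan gives no figure for the late weight comparisons, so there is none to reproduce. Missing fractions, correlations, SD and effect below are assumptions, shown with ranges.

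**1. Counts.** Postoperative visits: 3 (months 3, 6, 12) + 4 (years 2 to 5) = 7. Time points named for comparison: 4.

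**2. Precision at year 5.** Let m be the fraction missing at 5 years and r the correlation between adjacent visits (AR(1)). Drop-out is permanent and spread evenly over visits 2 to 7, so the fraction still seen at visit j is p_j = 1 − m(j − 1)/6. Variances are relative to complete data, with the covariance taken as known.

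- Attenders only: 1/(1 − m).
- Likelihood using all visits: v_1 = 1, then v_j = r²·v_(j−1) + (1 − r²)/p_j.

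For m = 0.3 and r = 0.8:

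- p = 1, 0.95, 0.90, 0.85, 0.80, 0.75, 0.70
- v = 1.000, 1.019, 1.052, 1.097, 1.152, 1.217, 1.293
- Attenders only: 1/0.7 = 1.429
- Reduction: 1 − 1.293/1.429 = 9.5%. Equivalently, 1.429/1.293 = 1.105, or about 10% more attenders.

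Reduction in year-5 variance over the grid:

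| Missing at 5 years | r = 0.7 | r = 0.8 | r = 0.9 |
|---|---|---|---|
| 20% | 3.6% | 6.0% | 10.7% |
| 30% | 5.7% | 9.5% | 16.4% |
| 40% | 8.2% | 13.3% | 22.5% |

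**3. Bias at year 5 (simulation).** There were 60 patients per arm (71 × 0.84 = 59.6), seven visits, SD 9 points of percentage weight loss, a true difference of 3 points, AR(1) correlation 0.7 or 0.9, and 250 replicates per scenario. Between 54% and 59% were still seen at 5 years, which is heavier loss than in step 2. The comparison is the attender-only mean difference against a maximum-likelihood repeated-measures model with arm-by-visit means and a common unstructured covariance. The Monte Carlo error of each bias is about 2.1/√250 = 0.13.

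| Drop-out mechanism | Attenders only, r = 0.7 / 0.9 | Model, r = 0.7 / 0.9 |
|---|---|---|
| Unrelated to weight | −0.12 / −0.02 | −0.10 / +0.07 |
| Last observed weight, both arms | −0.39 / −0.57 | +0.03 / +0.12 |
| Last observed weight, control arm only | −1.80 / −3.65 | +0.12 / −0.22 |
| Unobserved current weight, both arms | −0.46 / −0.84 | −0.29 / −0.37 |
| Unobserved current weight, control arm only | −2.84 / −3.81 | −1.68 / −1.00 |

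In the third row the attender-only bias removes more than half of the true 3 points at r = 0.7 and reverses the sign at r = 0.9; the model is close to unbiased. In the last row a share of the bias survives the model: 1.68/2.84 = 59% at r = 0.7 and 1.00/3.81 = 26% at r = 0.9.

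When drop-out is unrelated to weight, the SD of the estimate goes from 2.19 to 2.16 at r = 0.7 (variance down 3%) and from 2.15 to 1.82 at r = 0.9 (variance down 28%). This agrees with step 2 that the precision gain depends heavily on the correlation.

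**The case against.** The strongest reply is that the plan does not say it will do what is criticised. It nowhere restricts analyses to attenders, and it does not say that every visit will be tested. That is correct on both counts. The attender-only analysis follows by default from a t test with no missing-data rule; it is not a stated choice. The point stands on that narrower basis.

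Four stronger readings are tempting, and the documents or the arithmetic do not support them.

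- **That some 35 t tests are planned (7 visits × 5 derived measures).** This multiplies a measurement schedule by a list of variables. Only four postoperative time points are named for comparison.
- **That the model would cut the year-5 variance by 19% (range 10% to 32%).** The formula behind that figure, (1 − r²)/(1 − m) + r², gives 1.154 against 1.429 at m = 0.3 and r = 0.8. It needs every patient missing at year 5 to have been seen at the preceding visit. Patients who stop attending often miss several visits, and with even drop-out the gain is about half as large.
- **That the t test is unbiased only if attendance is unrelated to weight.** This is true of each arm's mean but too strong for the difference. With the same weight-dependent mechanism in both arms, the control mean was biased by +2.0 to +3.4 points (drop-out on the last observed weight), while the difference was biased by only −0.4 to −0.6. Large bias needs drop-out that differs by arm, which the documents do not predict.
- **That a mixed model cures the problem.** It does so only when drop-out depends on recorded weights.

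It is also fair to say that these are secondary, long-term results. None of these replies favours the t test for the late comparisons.

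**Conclusion.** The concern holds in limited form. Seven postoperative weights are scheduled and four time points are named for comparison, but the one method named uses a single visit at a time and nothing is said about missing weights.

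- **Precision:** a modest loss, 9.5% of the year-5 variance in the central case and 3.6% to 22.5% over the grid. This rests on AR(1) correlation, even permanent drop-out and assumed missing fractions.
- **Bias in the arm difference:** small if drop-out acts alike in both arms. It was −1.8 to −3.7 points on a true 3 when weight-related drop-out was confined to the control arm, under the simulation's assumed SD and retention. Whether this will occur cannot be judged from the documents.

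The main preoperative goal does not depend on these data and is unaffected. This is a worthwhile, low-cost improvement, not a threat to the trial's principal conclusion.

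**What to change.** In Statistical Analysis, replace the t test for the postoperative weight comparisons by one linear mixed model for repeated measures:

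- **Outcome:** one pre-specified weight-loss measure, for example %EWL, which the main criterion already uses.
- **Terms:** arm, visit, arm-by-visit and baseline weight, with unstructured covariance and a stated fallback if the model does not converge.
- **Baseline:** the weight measured 4 months before surgery. The day-of-surgery weight must not serve, because it follows the app period and is part of the primary outcome; adjusting for it would remove part of the effect under study.
- **Population:** all randomised patients with any postoperative weight, analysed in the arm to which they were allocated.
- **Report:** the arm difference with 95% CI at 3 months and at 1, 3 and 5 years.
- **Sensitivity analysis:** because the model relies on missing at random, add an analysis for drop-out that depends on unobserved weight. One option is to shift the imputed weights by a range of amounts, separately by arm, and report where the conclusion changes. Report the number weighed at each visit by arm.

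The cost is SAP wording and slightly more analysis work. No new data are needed. The text should be settled before the late weights are examined.

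### Do the March 2026 and March 2029 completion dates cut the 2-year and 5-year follow-up short?

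*Combined protocol and SAP*

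**What the plan says.** The calendar is in the Study duration part of section 1 (Resume) of the combined protocol and SAP:

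- The later of its two milestones reads "Long-term follow-up (5 years) will be completed in March 2029".
- The earlier milestone, for the yearly visits up to that point, reads "Mid-term follow-up (2 years) will be completed in March 2026".
- On accrual, the same part says "Patient recruitment period is expected from October 2022 to March 2024".
- It closes the preoperative phase with the operation itself.

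The visit schedule is under Evaluation criteria. There, "weight will be measured 4 months before surgery and on the same day of surgery; then at 3, 6 and 12 months"; annual measurements follow until the fifth year. Comorbidities, under the secondary criteria, "will be recorded to study their evolution up to 5 years after the intervention". The secondary goals use the same term, intervention, for the operation when they set the 30- and 90-day complication windows.

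Two other statements bear on the gap between recruitment and surgery. Study design says that patients randomised to the app receive it four months before their operation. The Chronogram allows 18 months for recruitment and a further 6 months for operations and follow-up together.

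**The concern.** The two completion dates look as if 2 and 5 years had simply been added to the month in which recruitment closes. Follow-up starts at surgery, and surgery comes some months after a patient joins. A patient recruited in the last month could therefore not have reached the 2- or 5-year visit by the printed dates.

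If the dates were treated as the end of data collection, the latest recruits would lack the final weight and comorbidity record. The 5-year weight belongs to a stated secondary hypothesis (1, 3 and 5 years), so the loss would touch a declared question. It would also fall on a recognisable group, those recruited last.

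**Working it through.** **Inputs.** Recruitment from October 2022 to March 2024 (Study duration), which is 18 months and agrees with the Chronogram. App given, and first weight taken, 4 months before surgery (Study design; Evaluation criteria). Further window of 6 months for operations and follow-up (Chronogram). Total sample 142, with 16% loss allowed (Sample size).

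**Step 1: reproduce the printed dates.**
- March 2024 + 24 months = March 2026.
- March 2024 + 60 months = March 2029.

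Both match exactly, with no lag between recruitment and surgery. The plan does not say how the dates were derived, so this origin is an inference from the match.

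**Step 2: insert the lag.** The 4 months are stated outright for the app arm. For controls they are inferred from the first weight, which is given without naming an arm.
- Last surgery: March 2024 + 4 = July 2024.
- 2 years: July 2024 + 24 = July 2026.
- 5 years: July 2024 + 60 = July 2029.

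At the printed dates the last recruit would be at postoperative month 24 − 4 = 20 and 60 − 4 = 56.

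**Step 3: how firm is the lag?** The Chronogram does not settle it.
- If all 6 months went to operations, the last surgery would be in September 2024 and the shortfall 6 months.
- If the window must also hold the 3-month follow-up, 6 − 3 = 3 months remain for operations, and the last surgery would be in about June 2024.
- That second reading conflicts with the 4-month lead, since 4 + 3 = 7 months exceeds 6.

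The shortfall is therefore about 3 to 6 months, with 4 the best-supported value.

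**Step 4: what depends on the dates?**
- Primary endpoint: preoperative, and complete on the day of surgery. Not affected.
- 30-day, 90-day and 3-month outcomes: complete by about October 2024 (July 2024 + 3). Not affected.
- 1- and 3-year weights: last due in July 2025 and July 2027, before March 2029. Not affected.
- 2-year visit: no hypothesis or goal names a 2-year outcome.
- 5-year visit: defined for each patient, with no calendar limit in the criteria.
- Statistical analysis and Sample size: neither refers to a calendar date, a lock or an interim look.

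**Step 5: the hypothetical loss.** Suppose follow-up were closed on the printed dates, accrual were even and the lag a constant 4 months. Then 4/18 = 22.2% of patients would lack the final visit: 142 × 0.222 = 31.6, about 32. After the planned 16% loss, 142 × 0.84 = 119.3, and 119.3 × 0.222 = 26.5, about 27. The plan states none of these three conditions, so these counts are not a forecast of missing data.

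**The case for a change.** The strongest case for acting is that the error is internal, needs no outside figure and is cheap to correct. The other readings fail. Counting from enrolment contradicts the follow-up of comorbidities to 5 years after the operation, and having every operation done by March 2024 contradicts the Chronogram's allowance for surgery after recruitment closes. Printed completion dates can also find their way into funding or archiving decisions, and the 5-year point is part of a secondary hypothesis.

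The mismatch itself stands. The consequence does not follow. Nothing in the plan tells anyone to stop collecting data in March 2026 or March 2029, and the passages that do govern collection say the opposite: each patient is seen up to 5 years. Staff who follow the visit schedule will obtain the 5-year weight whatever the milestone says. Even under an imposed closing date, no difference between the arms has been shown, since the 4-month preoperative interval appears to apply to both. New dates would themselves be uncertain, because the Chronogram's window and the 4-month lead do not fit together.

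**Conclusion.** The two completion dates are a clerical slip in a forecast: about 4 months early on the lag inferred from Study design and Evaluation criteria, and about 3 to 6 months early across the readings of the Chronogram. The size assumes that the last patient is recruited in March 2024 as expected and that follow-up runs from surgery.

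No change follows, because there is nothing to gain for the results. The dates trigger no cut, lock or analysis. The per-patient schedule already secures the 5-year data. The primary endpoint, sample size, short-term outcomes and 1- and 3-year points are untouched. An analyst would count each patient's follow-up from the date of surgery and reach the same conclusions whichever month is printed. The judgement would differ only if a document made those dates the end of data collection, and none does.

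### 71 per arm does not give the stated 80% power for a ≥ 5 kg loss in 55% vs 39%: two-sided power is about 42–48%

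*Combined protocol and SAP*

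**What the plan says.** The protocol's Sample size paragraph gives both the result and its inputs. The result: "The sample size was calculated in 142 patients divided into two groups of 71 patients each". The comparison: a "hypothetical reduction of ≥ 5 kg in 55% of patients in the C4T group vs in 39% of patients in the control group", with the rates referred to a cited systematic review. The loss allowance: "with a possible loss of 16% of patients". Confidence is set at 95% and power at 80%. Neither the formula nor the sidedness of the test is stated.

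Under Evaluation criteria, the main criterion is a different quantity: "Preoperative percentage of excess weight lost (%EWL), considering ideal BMI = 25, will be recorded". Under Statistical analysis, the tests are chi-square "for categoric variables and t test for continuous variables", and "A p value < 0.05 will be considered statistically significant". No mean difference or standard deviation for the percentage of excess weight lost (%EWL) appears anywhere.

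**The concern.** A 16-point difference between two proportions near 50% usually needs about 150 patients per arm for 80% power at a two-sided 5% level. A figure of 71 per arm is less than half of that, and it has to absorb a 16% loss as well.

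The 80% claim is the only justification given for enrolling 142 patients. If it is wrong, the trial could easily return a non-significant result even when the app works exactly as hypothesised. A reader who trusted the stated power might then take that result as evidence of no effect. The calculation also concerns a responder proportion while the main criterion is continuous, so even a correct figure would not show that the trial is adequately sized for its main goal.

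**Working it through.** **Inputs** (Sample size paragraph): p1 = 0.55, p2 = 0.39, difference 0.16, mean rate 0.47, 71 per arm, 16% loss, alpha 0.05, power 80%. Sidedness is not stated. I take two-sided as the usual reading of a chi-square test at p < 0.05 and show one-sided as well.

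**Trying to reproduce 71 per arm.** Pooled formula, evaluable patients per arm:

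n = [z_α √(2 · 0.47 · 0.53) + z_β √(0.55 · 0.45 + 0.39 · 0.61)]² / 0.16²

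- Two-sided: (1.960 × 0.7058 + 0.8416 × 0.6967)² / 0.0256 = (1.383 + 0.586)² / 0.0256 = 151.6, so 152. After loss, 152 / 0.84 = 181 per arm, 362 in total.
- One-sided: (1.645 × 0.7058 + 0.586)² / 0.0256 = 119.3, so 120. After loss, 120 / 0.84 = 143 per arm, 286 in total.

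| Variant | Two-sided n per arm | One-sided n per arm |
|---|---|---|
| Pooled | 151.6 | 119.3 |
| Unpooled | 148.8 | 117.2 |
| Arcsine | 151.4 | 119.3 |
| Continuity-corrected | 163.8 | 131.5 |

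None gives 71, before or after allowing for loss.

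**Power the design has for 55% vs 39%.** With losses, 71 × 0.84 = 59.6, about 60 evaluable per arm.

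Power = Φ{[0.16 √n − z_α × 0.7058] / 0.6967}

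| Evaluable per arm | Two-sided | Two-sided, exact chi-square | One-sided |
|---|---|---|---|
| 71 | Φ(−0.051) = 48.0% | 49.2% | 60.6% |
| 60 | Φ(−0.207) = 41.8% | 43.6% | 54.5% |

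**What 80% two-sided power would cover.** Solving the same formula against a control rate of 39% gives about 62% with 71 per arm and about 64% with 60. That is a difference of about 25 points in the latter case, not 16.

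**If the design rates were observed.** A chi-square test of the design comparison would have z = 0.16 / √(2 · 0.47 · 0.53 / n). This is 1.91 (p = 0.056) with 71 per arm and 1.76 (p = 0.079) with 60. With 60 per arm the 95% CI is 16 ± 17.6 points, about −2 to +34.

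**Main criterion, %EWL by t test.** Its power cannot be computed, because no difference or SD is given. The detectable standardised difference can be. At two-sided 5% and 80% power (noncentral t) it is 0.47 SD with 71 per arm and 0.52 SD with 60. For assumed SDs of 6 to 12 %EWL points (my range, not the protocol's), 0.52 SD is 0.52 × 6 = 3.1 to 0.52 × 12 = 6.2 points.

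**Illustration only.** If kilograms lost were normal with equal SDs, 55% vs 39% above a common cut-off would correspond to z(0.55) − z(0.39) = 0.126 + 0.279 = 0.405 SD. A t test on kilograms would then have 67% power with 71 per arm and 59% with 60, still below 80%.

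**The case against.** - **Sidedness is not stated.** True, but one-sided power is at most 61%, so the shortfall does not depend on it.
- **The ≥ 5 kg comparison is not a listed outcome.** This stands. The threshold appears only in the Sample size paragraph, so the p-values and interval above describe a chi-square test of the design comparison, not the planned main analysis. The rates are also not exactly attainable with 71 patients (39% of 71 is 27.7): 39 vs 28 responders gives p = 0.064, and 39 vs 27 gives p = 0.043. The power figures do not depend on this.
- **A continuous analysis could have more power.** Possibly, but the protocol gives nothing to show it, and the illustration above does not reach 80%.
- **The main criterion is itself not settled.** The list of comparisons under Study design names percentage of total weight lost, whereas Evaluation criteria labels %EWL as main. This stands as a point to reconcile before a power statement is written for either. It does not rescue the 80% claim.
- **An input may be misprinted.** The source of the rates cannot be checked from the documents. The printed figures are inconsistent either way.
- **Where 71 came from.** This cannot be inferred. The unrounded one-sided per-arm size after loss (119.27 / 0.84 = 142.0) equals the stated total. A one-sample, one-sided formula gives 58.2, rounded up to 59, and 59 / 0.84 = 70.2, rounded up to 71. Neither is a valid basis for 71 per arm in a two-arm comparison, and the documents mention neither.

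**Conclusion.** The concern holds. For the comparison named, the design has about 48% two-sided power if all 71 per arm are evaluable and about 42% after the planned loss (49% and 44% by exact chi-square), against the 80% stated. The stated total of 142 is about 40% of the 362 that the inputs require two-sided. The two-sided figures assume a two-sided 5% test; the failure to reach 80% does not. These results apply only to the ≥ 5 kg responder comparison. For %EWL the power is unknown rather than shown to be low, and no figure in the protocol supports it. This must be corrected, because it is the sole justification of the sample size.

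**What to change.** Keep 142 patients, remove the 80% power claim, and replace it with wording such as:

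> With 71 randomised and about 60 evaluable per arm (16% loss), two-sided 5% power for a ≥ 5 kg loss in 55% vs 39% is about 42% (48% without loss); 80% power is available for about 64% vs 39%. For the main criterion, %EWL compared by t test, 80% power is available for a mean difference of 0.52 SD (0.47 SD without loss), that is [x] points at an assumed SD of [y, with source].

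Before inserting the second sentence, confirm that %EWL is the main criterion and bring the list of comparisons under Study design into line. If any input was misprinted, correct it with its source and rerun the calculation. Report the primary effect with its 95% CI, so that a non-significant result is not read as no effect.

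The cost is one paragraph of wording and a sourced SD, with no extra patients; the downside is a less favourable stated power. If the sponsor instead wants 80% two-sided power for 55% vs 39%, that takes 362 patients, 220 more than planned.

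### 142 patients do not give the stated 80% power: 55% vs 39% needs 152 evaluable per arm, planned power is about 42–48%, and the main criterion (%EWL) has no power calculation

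*Combined protocol and SAP*

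**What the plan says.** All references are to the combined protocol and SAP, section 1 (Resume).

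- **Sample Size.** "The sample size was calculated in 142 patients divided into two groups of 71 patients each". The assumed effect is a "hypothetical reduction of ≥ 5 kg in 55% of patients in the C4T group vs in 39% of patients in the control group", "with a possible loss of 16% of patients, a confidence level of 95%, and statistical power of 80" percent. Neither the formula nor the sidedness of the test is given.
- **Statistical Analysis.** Chi-square for categorical variables and "t test for continuous variables". "A p value < 0.05 will be considered statistically significant".
- **Evaluation Criteria, main criterion.** "Preoperative percentage of excess weight lost (%EWL), considering ideal BMI = 25, will be recorded". Under the follow-up schedule, "weight will be measured 4 months before surgery and on the same day of surgery". Other weight measures follow, ending with "percentage of BMI lost, total weight and BMI lost". A rate of at least 5 kg lost is not among them, although it can be derived from the two weights.
- **Hypothesis.** The main hypothesis is directional: more preoperative weight loss with the app.
- **Study Design.** The list of comparisons names percentage of total weight loss before surgery, not %EWL.

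**The concern.** There are two separate problems.

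First, a difference of 16 percentage points near the middle of the scale is hard to detect with about 60 to 71 patients per arm. The stated 80% looked too high for the stated inputs, whichever standard formula was used.

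Second, the calculation is for a proportion, while the labelled main criterion is a continuous percentage to be compared by a t test. Even a correct calculation for the proportion would not give the power of the main comparison.

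The 80% figure is the only justification of N. A non-significant result read against it would be taken as fair evidence that the app adds nothing. If the true rates are 55% and 39%, the chance of missing the difference on the 5 kg measure is about 58% at 60 per arm, or 52% at 71, not 20%.

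**Working it through.** **Inputs.** p1 = 0.55, p2 = 0.39, difference 0.16, loss 16%, power 80%, 71 per arm (all from Sample Size); significance at 0.05 (Statistical Analysis). Two-sided testing is an assumption, consistent with a chi-square test at p < 0.05. One-sided testing is tried as well.

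**Step 1. Trying to reproduce 71 per arm.** With mean rate p̄ = 0.47, the pooled formula is

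n = [z_α √(2p̄(1−p̄)) + z_β √(p1(1−p1) + p2(1−p2))]² / (p1−p2)²

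Two-sided: [1.960 × √0.4982 + 0.842 × √0.4854]² / 0.0256 = (1.3834 + 0.5864)² / 0.0256 = 151.6, so **152 evaluable per arm**.

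| Formula | Two-sided n per arm | One-sided n per arm |
|---|---|---|
| Pooled | 152 | 120 |
| Arcsine | 152 | 120 |
| Unpooled | 149 | 118 |
| Continuity-corrected | 164 | 132 |

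Allowing for 16% loss:

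- Two-sided pooled: 152 / 0.84 = 181 per arm, 362 in total; 362 / 142 = 2.55.
- One-sided pooled: 120 / 0.84 = 143 per arm, 286 in total; 286 / 142 = 2.0.

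No two-sample version gives 71 per arm, before or after loss.

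**Step 2. Power at the planned size.** Evaluable patients after loss: 71 × 0.84 = 59.6, about 60 per arm.

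Power = Φ{[0.16√n − z_α √0.4982] / √0.4854}

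- n = 60, two-sided: Φ(−0.207) = 0.418
- n = 71, two-sided: Φ(−0.051) = 0.480

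| Method | 60 per arm | 71 per arm |
|---|---|---|
| Two-sided, normal approximation | 42% | 48% |
| Two-sided, exact enumeration of the uncorrected chi-square | 44% | 49% |
| Two-sided, exact enumeration with continuity correction | 36% | 42% |
| One-sided 0.05, normal approximation | 54% | 61% |
| One-sided 0.05, exact enumeration | 57% | 63% |

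**Step 3. What the size can detect.** Against 39% in controls, 80% power (two-sided) needs an app-arm rate of about 64% at 60 per arm (25 points) or 62% at 71 (23 points). The plan assumes 16 points.

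**Step 4. If the trial observed exactly the assumed rates.** z = 0.16 / √(0.4982 / n).

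- n = 60: z = 1.756, p = 0.079
- n = 71: z = 1.910, p = 0.056

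Neither is below 0.05. The nearest whole counts agree: 33/60 vs 23/60 gives p = 0.067, and 39/71 vs 28/71 gives p = 0.064.

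**Step 5. The main criterion, %EWL.** The documents give no difference or SD, so power can only be shown by assumed standardized difference (two-sided t test, 0.05):

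| Assumed difference | 60 per arm | 71 per arm |
|---|---|---|
| 0.3 SD | 37% | 43% |
| 0.4 SD | 58% | 66% |
| 0.5 SD | 78% | 84% |
| 0.6 SD | 90% | 94% |

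The difference detectable with 80% power is 0.52 SD at 60 and 0.47 SD at 71.

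**The case against.** Nobody can defend 71 per arm on these inputs. The serious objections concern what follows from that.

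- **A reporting slip may explain the figure.** The one-sided pooled formula gives 119.27 per arm, and 119.27 / 0.84 = 142.0. So 142 may be a per-arm number reported as the total. The match is close and fits the directional hypothesis, but the documents do not confirm it. It would explain the error, not remove it: 71 per arm would still be half of what that calculation requires. The sponsor should check.
- **Sidedness is not stated.** This is true, so the 2.5-fold shortfall depends on two-sided testing. On a one-sided reading it is about 2.0-fold, and the 80% still fails.
- **The low power belongs to a test the plan does not name as its main analysis.** This stands as a limit on the finding. The 42–48% applies to the 5 kg rate. For %EWL the power is unknown, not shown to be low.
- **The 5 kg rates do say something about a continuous measure.** If kilograms lost were normal with equal SDs, 55% vs 39% would correspond to 0.126 + 0.279 = 0.40 SD, with t-test power of about 59% at 60 per arm and 67% at 71. That is a useful anchor, but it rests on assumptions outside the plan, carries over only loosely to %EWL, and still falls short of 80%.
- **The plan already labels %EWL as main and gives the weighing times and the test.** This is largely so. What is missing is a statement of sidedness, the supportive status of the other weight measures, and a power basis.

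**Conclusion.** The sample size statement is wrong as written. For 55% vs 39% at two-sided 0.05, 80% power needs 152 evaluable per arm (149 to 164 across formulas), or 362 patients in total after 16% loss. The planned 142 give about 42% power with 60 evaluable per arm and 48% with 71. The two-sided basis is an assumption, but the conclusion does not depend on it.

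Separately, the stated power is for a rate that is not a named outcome, and the main criterion has no power basis at all. Its power could lie on either side of 80%, depending on a standardized difference that the documents do not give. This must be corrected, because the 80% is the only support for N.

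**What to change.** The correction below leaves N at 142.

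1. Withdraw the 80% power statement. State the power for 55% vs 39%: about 42% at 60 evaluable per arm and 48% at 71, two-sided 0.05.
2. In Statistical Analysis, name continuous preoperative %EWL, from the weight four months before surgery to the weight on the day of surgery, as the single primary endpoint, tested by a two-sided t test at 0.05. Label percentage of total weight loss, kilograms, BMI and any analysis of the 5 kg rate as supportive.
3. State power for %EWL from a sourced difference and SD. If there is no source, disclose as a limitation, not as a justification of N, that about 60 evaluable per arm detect about 0.52 SD with 80% power (0.47 SD at 71).
4. Minor: align the list of comparisons in Study Design with %EWL.

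**Cost.** Wording and one recalculation. Visits and data collection do not change, since both weights are already collected. The price is a less favourable stated power, and no claim of success on another weight measure.
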